9.5 Other Measures

9.5.1 Concomitant Medication

Medications will be coded using the WHO-DD Enhanced (v. WHO Drug Global B3 – Sep 2020 or later).

A medication will be considered concomitant if it has a start date on or after the first dose of study intervention or if it was started prior to the first dose of study intervention and was ongoing. If a medication has a partial or missing start/stop date and it is unclear from the date whether the medication was taken after the first dose of study intervention, then it will be considered concomitant.

For listings of medications, the following approach will be used to determine the Anatomical Therapeutic Chemical (ATC) term to be presented:

- If coded to level 4 then the level 4 coded term will be presented.
- If coding is not performed at level 4 but level 3 coding is present, then level 3 coded term will be presented.
- If coding is not performed at level 3 but level 2 coding is present, then the level 2 coded term will be presented.
- If coding is not performed at level 2 but level 1 coding is present, then the level 1 coded term will be presented.

The ATC term, preferred term, reported generic name and reported brand name will be listed for participants in the safety analysis set.

The start day and stop day will be included in the listing. In the case of partial dates, the missing components will be left blank. Completely missing start/stop dates will not be imputed.

9.5.2 Antiseizure medications, therapies and rescue medications

Prior and concomitant antiseizure medications will be listed separately by ATC term and preferred term.

The start day and stop day will be included in the listing. In the case of partial dates, the missing

components will be left blank. Completely missing start/stop dates will not be imputed.

The ATC term, preferred term, reported generic name or reported brand name will be listed.

9.5.3 Procedures and Non-Drug Therapies

Prior and concomitant procedures and non-drug therapies will be listed for all participants in the safety analysis set.

9.5.4 Plasma Concentrations of CBD and its Major Metabolites

At the indicated PK visits, a pre-dose sample will be collected within 60 minutes prior to the morning dose of the study intervention (*i.e.*, trough collection). The study intervention can then be administered during the visit once the pre-dose PK sample has been collected. At Visit 9 and Visit 20, additional PK samples will be collected at 3 and 6 hours after administration of the study intervention (each PK sampling time point will be separated by at least 2 hours).

Plasma concentrations of CBD and its major metabolites, 7-hydroxy-CBD (7-OH-CBD) and 7-carboxy-CBD (7-COOH-CBD), will be listed for all participants in the PK analysis set. Concentrations for each analyte will be summarized by the sample collection nominal timepoints for all participants in the PK analysis set.

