### **3.2. Cannabidiol Background**

GWP42003-P (Epidiolex/Epidyolex) is the substance code for the study intervention, purified GWP42003-P, a nonpsychoactive cannabinoid under development by Jazz Pharmaceuticals Research UK Ltd. for the treatment of a number of conditions. In the United States, Epidiolex is indicated for the treatment of seizures associated with LGS, DS, or TSC in patients 1 year of age and older. Epidyolex has received approval in the European Union for adjunctive use to treat seizures associated with LGS and DS, in conjunction with clobazam, in patients 2 years of age and older, and for adjunctive use to treat seizures associated with TSC in patients 2 years of age and older. The product has received Orphan Drug Designation from the European Medicines Agency (EMA) and US Food and Drug Administration (FDA) for the treatment of seizures associated with LGS, DS, and TSC.

GWP42003-P is extracted from *Cannabis sativa* L. plants, has a defined chemical profile, and contains consistent levels of cannabidiol (CBD) as the principal phytocannabinoid. Extracts from these plants are processed to yield pure ( $\geq 98\%$ ) CBD that typically contains less than 0.10% (w/w)  $\Delta^9$ -tetrahydrocannabinol (THC). The pure CBD is subsequently dissolved in excipients with added sweetener and flavouring.

The pharmacological effects of phytocannabinoids are thought to be mediated primarily via their interaction with the endocannabinoid system, which consists of cannabinoid receptors, endogenous ligands (endocannabinoids), and enzymes for endocannabinoid synthesis and degradation. Two G protein-coupled receptors for

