### **13.5. General Considerations**

Unless stated otherwise, continuous variables will be summarised showing the number of non-missing values (n), mean, standard deviation or standard error, median, interquartile range, minimum and maximum. Categorical variables will be summarised showing the number and percentage of participants in each category.

Summaries will be presented by indication and overall, unless otherwise specified.

For clinic visit-based endpoints (unless otherwise specified), baseline is defined as the last record or measure collected prior to the first dose of GWP42003-P.

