3.2 Sample Size and Power

Up to 27 participants will be assigned to receive the study intervention in order to achieve 18 evaluable participants, which the Pediatric Investigational Plan for GWP42003-P considers sufficient to characterize PK in children < 2 years of age. Enrolment will be stratified to ensure that at least 5 participants each with LGS and DS (1 to < 2 years of age) and 8 participants with TSC (4 participants < 1 year of age and 4 participants aged 1 to < 2 years) are included in this study, in order to achieve 18 evaluable participants. There will be no formal hypothesis testing and as such no formal sample size calculation has been performed. Evaluability is defined in Section 5.0 Analysis Populations.

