3.4 Method of Assigning Participants to Treatment Groups

Enrolment will be stratified via the Randomisation and Trial Supply Management (RTSM) to ensure that at least 5 participants each with LGS and DS (1 to < 2 years of age) and 8 participants with TSC (4 participants < 1 year of age and 4 participants aged 1 to < 2 years) are included in this study in order to achieve 18 evaluable participants. All participants will receive GWP42003-P in this nonrandomised study.

The RTSM will be used to manage study intervention supply. The RTSM system will be used at each clinic visit in order to:

- Obtain a participant's number.
- Obtain dispensing information.
- Provide completion/taper/premature termination information.

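### The SAP's plasma-concentration summary pools all enrolment strata, drops the protocol's indication and dose-level splits without recording it, and leaves children enrolled under 1 year visible only in listings

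*SAP*

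**What the plan says.** **Stratification.** SAP 3.2 asks for "at least 5 participants each with LGS and DS (1 to < 2 years of age", and SAP 3.4 for "8 participants with TSC (4 participants < 1 year of age and 4 participants aged 1 to < 2 years". Protocol 7.1 and 13.1 give the same quotas. The target is stated as "Up to 27 participants will be assigned to receive the study intervention in order to achieve 18 evaluable participants", a number that the Paediatric Investigational Plan "considers sufficient to characterize PK in children < 2 years of age".

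**PK output in the SAP.** Section 9.5.4 lists concentrations of CBD and its two metabolites per participant, then adds one summary: "Concentrations for each analyte will be summarized by the sample collection nominal timepoints for all participants in the PK analysis set". It names no grouping by age, indication or dose.

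**PK output in the protocol.** Section 13.5 sets the default: "Summaries will be presented by indication and overall, unless otherwise specified". Section 13.7.1.4 plans concentration summaries by nominal time, participant and dose level. It also sends the data to a population PK analysis, pooled with other studies and reported separately.

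**Listings.** SAP 7.3.1 lists age in months. SAP section 6 orders listings by site, indication and participant number, whereas SAP 11.2 says site and participant number only. Neither uses age or stratum.

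**Recorded changes.** SAP 9.6 reports the administrative discontinuation of 28 January 2025 and the move to listings. It does not mention the grouping of the PK summary.

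**The concern.** Exposure is a primary objective. SAP section 8 drops the efficacy evaluation and SAP section 9 reduces safety to listings, so the concentration table is the main numerical summary left. It pools children from 1 month to under 2 years at consent, three indications, and any dose the flexible schedule allows.

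The protocol treats infants under 1 year as a group apart. They have their own quota and their own exclusion concerning valproic acid (6.2.6), and the rationale in 3.3 mentions disease presenting before 12 months. They are also below the age in the US label, which the protocol describes as "indicated for the treatment of seizures associated with LGS, DS, or TSC in patients 1 year of age and older". A table that merges them with older children can hide a difference in exposure that a reader would want to see, and the PK listing as described carries no age or stratum column to help.

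**Working it through.** **1. The plan's own figure.** LGS 5 + DS 5 + TSC under 1 year 4 + TSC 1 to under 2 years 4 = 18, which reproduces the evaluable target. There is no power calculation to check: "There will be no formal hypothesis testing and as such no formal sample size calculation has been performed".

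**2. Share of the infant stratum at target.** 4/18 = 0.222, or 22%.

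**3. How far a difference would move the pooled summary.** Let r be the ratio of infant exposure to that of the other 14 children at the same dose. The documents give no r, so the values below are assumptions.

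- Pooled geometric mean relative to the other children: r^(4/18).
- Pooled arithmetic mean relative to the other children: (14 + 4r)/18.

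| Assumed r | Geometric | Arithmetic |
|---|---|---|
| 2 | 2^0.222 = 1.17 | (14 + 8)/18 = 1.22 |
| 0.5 | 0.5^0.222 = 0.86 | (14 + 2)/18 = 0.89 |

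The achieved share p is unknown. For r = 2 the geometric shift is 2^p, which is 1.07 at p = 0.10 and 1.41 at p = 0.50.

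**4. Dose range in the pooled table.** Protocol 8.1.2 sets a minimum of 2.5 mg/kg/day and maxima of 20 (LGS, DS) and 25 (TSC) mg/kg/day. Without a dose-level split, one cell can hold concentrations from doses up to 25/2.5 = 10-fold apart, and the permitted maximum itself differs by indication.

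**5. What an enrolment-age label means at sampling.** Age is fixed at consent. Postdose samples are taken at Visit 9 (Day 57) and Visit 20 (Day 365), after 28 days of screening.

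- Visit 20: 28 + 364 = 392 days; 392/30.4375 = 12.9 months. A child consented at 1 month is then about 13.9 months old, so no on-schedule Visit 20 sample comes from a child under 1 year.
- Visit 9: 28 + 56 = 84 days = 2.8 months. Only children consented before about 9.2 months are still under 1 year.

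A column headed simply as under 1 year would therefore mislabel the on-schedule Visit 20 data. It has to be labelled as age at enrolment.

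**6. Precision of a split table.** The 95% t-interval half-width for a mean, in SD units, is t(0.975, n − 1)/√n: 0.50 at n = 18, 1.24 at n = 5, 1.59 at n = 4, 2.48 at n = 3 and 8.98 at n = 2. Stratum cells can describe but not estimate.

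**The case against.** The strongest reply is that nothing is lost. Concentrations and age in months are both listed per participant. DS and LGS children must be at least 1 year old at consent, so any child enrolled under 1 year has TSC. With so few children, a reader can pick them out by participant number. This stands, and it limits the point to the summary table and the columns of the listing. A reader might infer that the infants' data cannot be seen at all; the documents do not support that.

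A reader might also infer that the SAP removed a planned age analysis, or that the exposure objective is specifically about the youngest children. Neither is in the text. The protocol never planned an age split, the objective names no age group, and the 18 is justified for children under 2 years as a whole. What the SAP removed is the split by dose level and the default split by indication. The default in 13.5 allows exceptions, so 13.7.1.4 could be read as replacing it for PK; the dose-level split is then still dropped without a note.

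Four further replies have some force:

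- The study was terminated, and the infant stratum may hold fewer than 4 children, perhaps none. The 4 in 18 mix is only the target.
- The pooled summary also gives SD, quartiles, minimum and maximum (SAP 4.1), so an outlying group need not vanish entirely. These statistics do not say which children lie at the extremes.
- The population PK analysis may examine age. The documents do not say so, and it is reported separately.
- The table shells are a separate document not available here and may already group the table. The SAP text should still state the grouping.

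**Conclusion.** The point holds as a gap in one summary and in the record of changes. SAP 9.5.4 pools a primary endpoint across the strata that enrolment was designed to fill, departs from protocol 13.5 and 13.7.1.4, and does not say so in 9.6. At the target mix and an assumed 2-fold ratio in either direction, the pooled geometric mean shifts by a factor of only 1.17 or 0.86, so the summary would largely mask such a difference. This rests on the planned 4 of 18, equal dosing across groups and an illustrative ratio; the achieved mix is not given.

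It would go too far to call this the only numerical summary. SAP 6.1.9.4 also says that dosing days will be summarised, although 7.4 only lists them. No conclusion of the study is invalidated. The change is a cheap improvement in how readable the exposure result is.

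**What to change.** - **SAP 9.5.4:** present the concentration summary by indication and, within TSC, by age stratum at enrolment, beside the pooled column. Label the age split explicitly as age at enrolment. Show n, median and range, and refer to the listing where a cell is too small to summarise.
- **PK listing:** add enrolment stratum and age in months at sampling as columns.
- **SAP 9.6:** record that the PK summary departs from the grouping by indication in protocol 13.5 and by dose level in 13.7.1.4, with the reason.

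The cost is a few lines of SAP and shell text. The stratum is already held in the RTSM; age at sampling has to be derived. The downside is very small cells (4 or 5 per stratum at full quota, possibly fewer after early termination), so the split columns are descriptive only and should carry no inference.

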9.5.5 Dosing and food intake

Morning and evening dosing from the eDiary will be listed for all participants in the screening analysis set.

Mealtime and food diary data will be listed for all participants in the screening analysis set.

9.6 Changes in the Conduct of the Trial or Planned Analysis

Due to poor recruitment and retention, a decision was made to administratively discontinue the study on 28 January 2025. To support the production of a synoptic CSR, a pre-specified set of collected data will be listed.

10. References

1. US Federal Register. (1998) International Conference on Harmonization; Guidance on Statistical Principles for Clinical Trials. Department of Health and Human Services: Food and Drug Administration [Docket No. 97D-0174]. Federal Register Volume 63, Number 179, pages 49583-49598. September 16, 1998.
2. ASA. (2016) Ethical Guidelines for Statistical Practice. Prepared by the Committee on Professional Ethics, April 2016. <http://www.amstat.org/about/ethicalguidelines.cfm>
3. RSS. (2014) The Royal Statistical Society: Code of Conduct, 2014. <http://www.rss.org.uk/Images/PDF/join-us/RSS-Code-of-Conduct-2014.pdf>.

4. HealthActCHQ. (2018). ITQOL: Infant Toddler Quality of Life Questionnaire
5. QualityMetric Incorporated, LLC. (2011-2023). ITQOL: Infant and Toddler Quality of Life Questionnaire (ITQOL-SF47TM) Parent Short Form – 47 Italy (Italian)

11. Tables, Listings and Figures

All outputs will have a header showing the sponsor company name and protocol and a footer showing the version of SAS, the file name and path, and the source of the data (CRF page or listing number).

There are no planned figures for the abbreviated CSR.

11.1 Planned Table Descriptions

Planned summary tables for protocol GWEP17005 are described in separate shells documentation. Tables are numbered according to the nomenclature used to support the CSR and according to Jazz standards.

11.2 Planned Listing Descriptions

Planned listings for protocol GWEP17005 are described in separate shells documentation. Listings are numbered according to the nomenclature used to support the CSR.

All listings will be sorted by site and participant number.

In all listings a blank line will be placed between each participant. Within a data listing, if an item appears line after line (e.g., repetition of participant number), then only the first occurrence will be displayed.

In data listings, the information for one participant will be kept on one page, if at all possible, rather than splitting a participant's information across pages.

Tables, Listings, and Listing Shells

11.3 Standard Layout for all Tables and Listings

Table and listing shells are provided as a separate document. The final statistical tables will be produced in the format of the shells and will additionally include “double” page numbering in the format “page xx of yy”. Note that programming notes may be added or modified if appropriate after each shell.

The final statistical output will be provided as fully bookmarked pdf file including a table of contents.

APPENDIX 1 Abbreviations

Abbreviation	Definition
AE	Adverse Event
ALQ	Above the Limit of Quantification
ASM	Antiseizure Medication
BLQ	Below the Limit of Quantification
CBD	Cannabidiol
COVID-19	Coronavirus Disease 2019
CRO	Contract Research Organization
CSR	Clinical Study Report
D	Day
DS	Dravet Syndrome
ECG	Electrocardiogram
eCRF	Electronical Case Report Form
EDRS	Epilepsy Diary Reference Sheet
EEG	Electroencephalogram
ePRO	Electronic Participant Reported Outcome
EMA	European Medicines Agency
EOT	End of Treatment
ESCI	The Epilepsy Study Consortium
ET	Early Termination
FDA	Food and Drug Administration
ICF	Informed Consent Form
ICH	International Conference on Harmonisation
ILAE	International League Against Epilepsy
IMP	Investigational Medicinal Product
ITQOL-SF47	Infant Toddler Quality of Life Questionnaire – Short Form 47
LGS	Lennox-Gastaut Syndrome
MedDRA	Medical Dictionary for Regulatory Activities
PK	Pharmacokinetics
QTcB	QT-interval for ECG Corrected for Heart Rate Using Bazette's Formula
QTcB	QT-interval for ECG Corrected for Heart Rate Using Fridericia's Formula
RTSM	Randomization and Trial Supply Management
SAE	Serious Adverse Event
SAP	Statistical Analysis Plan
SD	Standard Deviation
SIF	Seizure Identification Form
SMC	Safety Monitoring Committee
SOC	System Organ Class
TEAE	Treatment-Emergent Adverse Event
TSC	Tuberous Sclerosis Complex
VEEG	Video Electroencephalogram
WHO	World Health Organization

APPENDIX 2 Ranges for Clinically Significant Changes and Other Defined Flagged Values in Vital Signs

The range of values that will be used to identify clinically significant changes in vital signs parameters (See Section 9.3.1) are presented in Table 3. Ranges for Potentially Clinically Significant Changes in Vital Signs.

Table 3. Ranges for Potentially Clinically Significant Changes in Vital Signs

Vital Sign	Range
Supine Systolic BP (mmHg)	Change: < -20, > 20
Supine Diastolic BP (mmHg)	Change: < -10, > 10
Pulse Rate (beats/min)	Change: < -10, > 10

Defined flagged values that will be used to identify low or high vital signs parameters (See Section 9.3.1) are presented in Table 4. Other Defined Flagged Values for Vital Signs

Table 4. Other Defined Flagged Values for Vital Signs

Vital Sign	Flag
Supine Systolic BP (mmHg)	< 70, > 121
Supine Diastolic BP (mmHg)	< 32, > 76
Pulse Rate (beats/min)	< 95, > 210
Temperature (°C)	> 38.0, < 35.5
Respiratory Rate (breath/min)	< 15, > 53

APPENDIX 3 Defined Flagged Values in ECG Parameters

Defined flagged values that will be used to identify low or high ECG parameters (See Section 9.3.2) are presented in Table 5. Defined Flagged Values for ECG Parameters

Table 5. Defined Flagged Values for ECG Parameters

ECG Parameter	Flag
QTcB (msec)	> 460

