## LIST OF ABBREVIATIONS

7-COOH-CBD	7-carboxy-cannabidiol
7-OH-CBD	7-hydroxy-cannabidiol
ACTH	Adrenocorticotropic hormone
AE	Adverse Event
ALT	Alanine aminotransferase
ASM	Antiseizure medication
AST	Aspartate aminotransferase
b.i.d.	Twice a day
CBD	Cannabidiol
CBD-OS	Cannabidiol oral solution
CB1	Cannabinoid receptor 1
CB2	Cannabinoid receptor 2
CFR	Code of Federal Regulations
CGIC	Clinician Global Impression of Change
CGIS	Clinician Global Impression of Severity
CIOMS	Council for International Organizations of Medical Sciences
COVID-19	Coronavirus disease 2019
CRO	Clinical Research Organisation
CSR	Clinical Study Report
CTIS	Clinical Trials Information System
DRF	Diagnostic Review Form
DS	Dravet syndrome
ECG	Electrocardiogram
eCRF	Electronic case report form
EC	Ethics Committee
EDC	Electronic data capture
EDRS	Epilepsy Diary Reference Sheet
EEG	Electroencephalogram
EMA	European Medicines Agency
EOT	End of treatment
ePRO	Electronic patient-reported outcome
ES	Epileptic spasms
ESCI	Epilepsy Study Consortium
ET	Early termination
EU	European Union
EU CTD	European Union Clinical Trial Directive

EU CTR	European Union Clinical Trial Register
EudraCT	European Union Drug Regulating Authorities Clinical Trials Database
FDA	Food and Drug Administration
G	Gastric
GCP	Good Clinical Practice
GGT	Gamma-glutamyl transferase
G-tube	Gastric-tube
GW	GW Research Ltd
GWP42003-P	Cannabidiol oral solution
IB	Investigator's Brochure
ICF	Informed consent form
ICH	International Council for Harmonisation of Technical Requirements for Human Use
IEC	Independent Ethics Committee
ILAE	International League Against Epilepsy
INR	International Normalised Ratio
IRB	Institutional Review Board
IS	Infantile spasms
ITQOL-SF47	Infant and Toddler Quality of Life-Short Form 47
LAR	Legally authorised representative
LGS	Lennox-Gastaut syndrome
mTOR	Mammalian target of rapamycin
NG	Nasogastric
PI	Principal investigator
PK	Pharmacokinetic
PLN	Packaging lot number
PT	Prothrombin time
QoL	Quality of life
QTcB	Corrected QT interval with Bazett correction
RTSM	Randomisation and Trial Supply Management
SAE	Serious Adverse Event
SAP	Statistical analysis plan
SCN1A	Sodium voltage-gated channel alpha subunit 1
SE	Status epilepticus
SEGA	Subependymal giant cell astrocytoma
SEN	Subependymal nodules
SIF	Seizure Identification Form

SMC	Safety monitoring committee
SoA	Schedule of Activities
SOC	System Organ Class
SUSAR	Suspected Unexpected Serious Adverse Reaction
TBL	Total bilirubin

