9.3.3 ECG

ECG data will be listed for all participants in the safety analysis set. ECG data include mean heart rate, RR interval, PR interval, QRS duration, QT interval, QTcB and QTcF and whether potentially clinically significant based on criteria given in APPENDIX 3.

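### The only ECG flag is an absolute QTcB limit; with no change-from-baseline criterion, a sizeable QTc rise can go unmarked in the ECG listing

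*SAP*

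**What the plan says.** The 12-lead ECG is one of the primary safety endpoints (Protocol Section 2; SAP 2.2.1).

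- **ECG listing.** SAP 9.3.3 lists ECG data for the safety analysis set. Besides heart rate, the listing covers "RR interval, PR interval, QRS duration, QT interval, QTcB and QTcF and whether potentially clinically significant based on criteria given in APPENDIX 3".
- **ECG criterion.** SAP Appendix 3 describes Table 5 as "Defined flagged values that will be used to identify low or high ECG parameters". Its single row is "QTcB (msec) > 460". There is no lower limit, no QTcF limit and no limit on change.
- **Vital signs, by contrast.** SAP Appendix 2 gives two kinds of flag. Table 3 has change limits, for example "Pulse Rate (beats/min) Change: < -10, > 10". Table 4 has absolute limits, for example "Pulse Rate (beats/min) < 95, > 210".
- **Baseline.** SAP 6.1.2 defines baseline for safety endpoints, naming the ECG, as the last non-missing value before first dose.
- **Labels.** The Protocol abbreviation list gives QTcB as "Corrected QT interval with Bazett correction". SAP Appendix 1 has two entries for QTcB, the second with Fridericia's definition. SAP Appendix 3 points back to Section 9.3.2, which is Physical Examination; ECG is 9.3.3.

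**The concern.** A single absolute limit ignores where each child started. A child with a low baseline can have a large rise without crossing it, while a child who starts near it needs only a small one. The SAP recognises this for vital signs, where it flags change, but not for the ECG.

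The second issue is heart rate. Bazett and Fridericia diverge as the rate moves away from 60 bpm, and infants' rates lie well above that: Table 4 leaves 95 to 210 bpm unflagged. One QTcB limit therefore corresponds to different QTcF values in different children, or in one child whose rate changes over the planned 52 weeks.

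The abbreviated SAP replaces the ECG summaries planned in Protocol 13.7.1.3 with listings. The Appendix 3 marker is then the only pre-specified interpretation of the ECG data, and it determines which participants stand out on a primary safety endpoint.

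**Working it through.** The 460 ms limit is stated without derivation, so there is no planned figure to reproduce. The checks ask what the limit does and does not mark.

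**Inputs.** From the documents: QTcB > 460 ms (SAP Table 5) and the unflagged pulse range of 95 to 210 bpm (SAP Table 4). Baseline QTc values and heart-rate paths are not in the documents; those used below are assumptions.

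**Formulas.** With RR = 60/HR in seconds, QTcB = QT / RR^(1/2) and QTcF = QT / RR^(1/3). Hence QTcF = QTcB × (60/HR)^(1/6).

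**1. Largest rise in QTcB that is never marked: 460 − baseline**

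| Assumed baseline QTcB (ms) | Largest unmarked rise (ms) |
|---|---|
| 380 | 80 |
| 400 | 60 |
| 420 | 40 |

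This result does not depend on the choice between Bazett and Fridericia.

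**2. What the QTcB limit means on the Fridericia scale: 460 × (60/HR)^(1/6)**

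| HR (bpm) | QTcF at QTcB = 460 (ms) |
|---|---|
| 95 | 426.1 |
| 120 | 409.8 |
| 150 | 394.9 |
| 180 | 383.0 |
| 210 | 373.3 |

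The spread is 426.1 − 373.3 = 52.8 ms. Put the other way, a fixed QTcF of 400 ms crosses QTcB 460 at HR = 60 × (460/400)^6 ≈ 139 bpm. It is marked above that rate and not below.

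**3. One child whose heart rate falls (assumed 150 to 110 bpm, baseline QTcB 420)**

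- Baseline QTcF: 420 × (60/150)^(1/6) = 360.5 ms.
- Later QTcB of 459, just under the limit: QTcF = 459 × (60/110)^(1/6) = 414.9 ms.
- Change in QTcF: 414.9 − 360.5 = 54.4 ms. Change in QTcB: 459 − 420 = 39 ms. Nothing is marked.

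**4. Would a change flag on QTcB be enough?** On the same path, a QTcF rise of 30 ms (360.5 to 390.5) gives QTcB = 390.5 / (60/110)^(1/6) ≈ 432, a rise of only about 12 ms. A change criterion on QTcB alone would absorb part of the shift, so the criterion should use QTcF or be read with heart rate.

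**5. Does the duplicated label matter?** Read as Bazett, a limit of 460 is a raw QT of 365.6 ms at 95 bpm and 245.9 ms at 210 bpm. Read as Fridericia, it is 394.7 and 303.0 ms. The two readings differ by 29.1 and 57.1 ms.

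**The case against.** The strongest reply is that little is lost. Heart rate, RR, QT, QTcB and QTcF are all listed for every participant in the safety set, so a reader can work out the change. Protocol 9.1.8 requires a physician to review each ECG immediately and to record clinically significant abnormal findings. Exclusion criteria 6.2.9 and 6.2.10 keep out children with clinically significant ECG abnormalities or with cardiovascular conditions that would interfere with ECG assessment. Protocol 13.7.1.3 promises change from baseline for vital signs only, so the SAP does not depart from the protocol. The study was terminated, at most 27 treated participants were planned, and nothing is tested. All of this stands and limits the severity.

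Table 3 would also mark a 40 bpm fall in pulse if the vital-sign pulse moved with the ECG rate. That is true, but the mark sits in a different listing and says nothing about QT.

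Three stronger readings are tempting and are not supported:

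- **That Bazett produces false positives in fast hearts and false reassurance later.** This needs Fridericia to be the right reference in infants. Neither document says so. The arithmetic shows that the two corrections diverge, not which one is wrong.
- **That heart rate will fall by a known amount, or that 53 ms is a within-child effect.** The documents give no expected heart-rate course. The 53 ms compares the two ends of the unflagged range. With QTcB held at 440, assumed falls of 140 to 120 and 150 to 110 bpm shift QTcF by 9.9 and 20.0 ms.
- **That SAP 9.3.3 promises a flag for every ECG parameter.** It lists the parameters and refers to Appendix 3 for the criteria. It does not undertake to give one for each.

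**Conclusion.** The point holds as a minor one. Table 5 has a single absolute criterion and no change criterion, unlike the vital-sign tables. As a result, QTcB rises of 40 to 80 ms from assumed baselines of 420 to 380 ms go unmarked. On an assumed heart-rate fall from 150 to 110 bpm, so does a QTcF rise of 54 ms. The first result rests only on the assumed baselines. The second also rests on the assumed heart-rate path and on taking Fridericia as the comparison scale.

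The consequence is a missing marker in a by-participant listing. No ECG data are concealed, and no estimate or inference is biased. The duplicated QTcB definition and the wrong section reference are plain errors. SAP 9.3.3 names QTcB and QTcF separately, and the Protocol defines QTcB as Bazett, so the intended reading of the flag is reasonably clear.

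**What to change.** In SAP Appendix 3, Table 5:

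1. Keep QTcB > 460 ms as it is.
2. Add flags for change from baseline in QTcF, using the baseline in SAP 6.1.2. Suggested cut-offs are > 30 ms and > 60 ms. These are a proposal and are not in the documents, so the sponsor should confirm or replace them. The 54 ms example would trip the first but not the second.
3. Show heart rate beside each flagged value. It is already in the listing.
4. Treat an absolute QTcF limit as optional; if one is added, the sponsor should state and justify it.

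Also correct the second QTcB entry in SAP Appendix 1, which should read QTcF, and change the reference in Appendix 3 from Section 9.3.2 to 9.3.3.

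The cost is a few extra columns in an existing listing and some additional flags to review. No new data are needed. These are reporting flags and change nothing in how participants are managed.
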